All sleep variables will be assessed by the CSDI and the Sleep and Nap Diary, and will be summarized at baseline and after 13, 26 and 39 weeks of Circadin® open-label treatment (Weeks 28, 41 and 54, actual change from baseline) for each treatment group using descriptive statistics (n, mean, SD, median, minimum, and maximum). CSDI will be also summarized after 106 and 108 weeks of Circadin® open-label treatment.

CGAS score will be summarized at baseline and after 13 weeks of Circadin® open-label treatment (Week 28; actual change from baseline) for each treatment group using descriptive statistics (n, mean, SD, median, minimum, and maximum).

The SDQ score will be summarized at baseline and after 13 weeks of Circadin® open-label treatment (Week 28; actual change from baseline) for each treatment group using descriptive statistics (n, mean, SD, median, minimum and maximum).

The ESS score for the parent and caregiver will be summarized at baseline and at the 5, 15, 28, 41, 54, 106 and 108 week time points (actual change from baseline) using descriptive statistics (n, mean, SD, median, minimum, and maximum). Note: The ESS is to assess the sleepiness of the parent/caregiver and NOT the child.)

The WHO-5 score (parent's well-being assessment) will be summarized at baseline and at the 5, 15, 28, 41, 54, 106 and 108 week time points (actual change from baseline) using descriptive statistics (n, mean, SD, median, minimum, and maximum). Note: The WHO-5 is to assess the quality of sleep of the parent/caregiver and NOT the child.)

The PSQI global score and components (parent's sleep variables) will be summarized at baseline and at the 5, 15, 28, 41, 54, 106 and 108 week time points (actual change from baseline) using descriptive statistics (n, mean, SD, median, minimum, and maximum). Note: The PSQI is to assess the quality of sleep of the parent/caregiver and NOT the child.)

For all exploratory analyses for the double-blind period, a MMRM will be fitted to assess any differences in treatment effects over time. The base models will contain the specified outcome measure after baseline as the dependent variable, with independent variables in the form of the

baseline score, the study visit (categorical variable) and treatment allocation.

Safety Analyses

Secondary Safety Endpoints

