- The Sleep and Nap Diary is to be completed only by the patient's parent/caregiver during the 14 nights before each scheduled visit, every morning 2 to 3 hours after the child awakens ([Appendix 1](#) and [Appendix 2](#)). The diary can be completed either directly in the eCRF or by using a paper version. If the diary is completed on paper, the site coordinator will enter the questionnaire data into the eCRF during the visit. The diaries prior to Visit 1 and Visit 2 must be entered in to the system at the respective visit in order to allow eligibility assessment to occur at Visit 1 and Visit 2. Prior to Visit 1, diaries are required only for children who had undergone the 4-week sleep hygiene and behavioral intervention training period, to check whether they responded to the therapy. Diaries prior to Visit 1 are not required for children with a documented history of sleep hygiene and behavioral intervention, as Visit 1 eligibility for these children is measured based on the parent's report of their child's sleep over the previous 3 months, which is reported at screening. If the child doesn't need the sleep hygiene but needs the 2-week wash-out period prior to Visit 1, the parent doesn't need to complete the sleep diary either.
- For patients with epilepsy and a history of seizures, the Epilepsy Seizures Diary is to be dispensed to the parents/caregivers at each visit and to be completed by the patient's parent/caregiver only on the days that the patients has a seizure. It should include the date, time, duration and type of the seizure ([Appendix 10](#)). The Epilepsy Seizures Diary is to be completed only by the patient's parent/caregiver after each seizure.
- The questionnaires CSDI, SDQ, ESS, WHO-5, and PSQI are to be completed by the site coordinators/Investigators with the parents/caregiver, by posing the questions in the questionnaires and filling in the responses given by the parents/caregiver. Note: The ESS, WHO-5, and PSQI are to assess sleepiness, quality of sleep, and well-being of the parent/caregiver and NOT the child.
- The TESS ([Appendix 5](#)) and CGAS ([Appendix 3](#)) must be administered and completed by the Investigator with the parent/caregiver's input.

The following table ([Table 8-1](#)) identifies to whom the questionnaire relates and who is responsible for completing the questionnaire.

Table 8-1: Summary of Questionnaires

Questionnaire	Information relates to:	Completed by:
Sleep and Nap Diary	Child	Parent/caregiver

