Appendix 7: Epworth Sleepiness Scale

This is to be completed by the site coordinator/Investigator with the parent/caregiver's input. Note: The ESS is to assess sleepiness of the **parent/caregiver** and NOT the child.

Site:	
Subject number:	
NEU_CH_7911 - Epworth Sleepiness Scale (ESS)	
	
Was the Epworth Sleepiness Scale questionnaire completed?	 Yes  No
Date of assessment	
Questionnaire completed by	 Mother  Father  Guardian  Caregiver  Other
If completed by other, please specify	
Likelihood of dozing or falling asleep:	
Sitting and reading	 Would never doze  Slight chance of dozing  Moderate chance of dozing  High chance of dozing
Watching TV	 Would never doze  Slight chance of dozing  Moderate chance of dozing  High chance of dozing
Sitting, inactive in a public place (e.g., a theatre or a meeting)	 Would never doze  Slight chance of dozing  Moderate chance of dozing  High chance of dozing
As a passenger in a car for an hour without a break	 Would never doze  Slight chance of dozing  Moderate chance of dozing  High chance of dozing
Lying down to rest in the afternoon when circumstances permit	 Would never doze

Site:

Subject number:

NEU_CH_7911 - Epworth Sleepiness Scale (ESS)

	 Slight chance of dozing  Moderate chance of dozing  High chance of dozing
Sitting and talking to someone	 Would never doze  Slight chance of dozing  Moderate chance of dozing  High chance of dozing
Sitting quietly after a lunch without alcohol	 Would never doze  Slight chance of dozing  Moderate chance of dozing  High chance of dozing
In a car, while stopped for a few minutes in the traffic	
Total (calculated)	

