Appendix 8: Pittsburgh Sleep Quality Index

This is to be completed by the site coordinator/Investigator with the parent/caregiver's input. Note: The PSQI is to assess the well-being of the **parent/caregiver** and NOT the child.

Site: Subject number: NEU_CH_7911 - Pittsburgh Sleep Quality Index (PSQI)		
Was the Pittsburgh Sleep Quality Index questionnaire completed?	 Yes  No	
Date of assessment		
Time of questionnaire		
Questionnaire completed by	 Mother  Father  Guardian  Caregiver  Other	
If completed by other, please specify		
1. During the past two weeks, what time have you usually gone to bed at night?		
2. During the past two weeks, how long (in minutes) has it usually taken you to fall asleep each night?		
3. During the past two weeks, what time have you usually gotten up in the morning?		
4. During the past two weeks, how many hours of actual sleep did you get at night? (This may be different than the number of hours you spent in bed)		
5. During the past two weeks how often have you had trouble sleeping because you...		
a. cannot get to sleep within 30 minutes	 Not during the past two weeks  Less than once a week  Once or twice a week  Three or more times a week	
b. wake up in the middle of the night or early morning	 Not during the past two weeks  Less than once a week  Once or twice a week  Three or more times a week	

Site:

Subject number:

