10.6 Prior and Concomitant Medications

Concomitant medications recorded during the study will be coded using World Health Organization (WHO)-Drug. Details of concomitant medication will be listed.

Concomitant medications will be summarized according to whether they were being taken pre-study (prior medications) and/or during the study (concomitant medication). Prior medications are any that were being taken prior to the first dose of study medication (medication stop date prior to the first dose of study medication). Concomitant medications are any that were being taken on or after the first dose of study medication. If the start and stop dates of the concomitant medications do not clearly define the period during which a medication was taken, it will be assumed to be a concomitant medication.

Concomitant medications will be assigned to the phase they were taken: Double-Blind, first Open-Label, second Open-Label. If a concomitant medication starts or is ongoing between Visit 2 and Visit 4, it will be assigned to the Double-Blind phase. If a concomitant medication starts or is ongoing between Visit 4 + 1 day and Visit 5, it will be assigned to the first Open-Label phase. If a concomitant medication starts or is ongoing between Visit 5 + 1 day and Visit 8, it will be assigned to the second Open-Label phase. If the start and stop dates of the concomitant medications do not clearly define the phase during which a medication was taken, it will be assumed to be taken across all phases.

Prior and concomitant medications will be summarized by Anatomical Therapeutic Chemical (ATC) level 2 term and preferred term.

Details of non-pharmacological concomitant measures will be listed.

11 Efficacy

Subjects will be classified and summarized by randomized treatment. For all efficacy assessments, the baseline values will be calculated as the last recorded value prior to the start of randomized treatment. Change from baseline values will be calculated as the assessment score minus the baseline value. For questionnaires the change from baseline values will be calculated for each item and total/subscale score as applicable.

All summaries and analyses will be performed on the FAS set. The primary efficacy endpoint and select secondary efficacy endpoints will also be analyzed on the PP set. Analyses looking at the impact missing data on the primary efficacy endpoint will also be performed on the All Randomized set.

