11.3.5 ESS

Caregiver sleepiness as assessed by the ESS total score and the change from baseline in ESS total score will be summarized by scheduled visit using descriptive statistics. The ESS total score after 3 weeks and 13 weeks of double blind treatment and during open-label treatment will be analysed as detailed above for TST.

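### ESS, PSQI and WHO-5 measure the adult who answers, and neither document keeps that adult the same across visits or says what to do if a different one answers

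*Protocol*

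**What the plan says.** Protocol Section 8 states who supplies the answers: "The questionnaires CSDI, SDQ, ESS, WHO-5, and PSQI are to be completed by the site coordinators/Investigators with the parents/caregiver". It also states whose condition is measured: "Note: The ESS, WHO-5, and PSQI are to assess sleepiness, quality of sleep, and well-being of the parent/caregiver and NOT the child". Table 8-1 likewise lists all three scales as relating to the parent. The PSQI items (Appendix 8) address the respondent directly, for example "During the past two weeks, what time have you usually gone to bed at night", and the WHO-5 items (Appendix 9) are in the first person.

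Each of the three forms carries the field "Questionnaire completed by" with the options mother, father, guardian, caregiver and other, followed by "If completed by other, please specify".

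For analysis, the Protocol Synopsis says "The ESS score for the parent and caregiver will be summarized at baseline" and then at Weeks 5 to 108 as change from baseline. PSQI and WHO-5 are treated alike. SAP Section 9.3 defines baseline as the last value before randomised treatment. SAP Section 11 adds: "Change from baseline values will be calculated as the assessment score minus the baseline value". SAP 11.3.5 says: "Caregiver sleepiness as assessed by the ESS total score and the change from baseline in ESS total score will be summarized by scheduled visit". It then sends the ESS total through the TST analysis, as 11.3.6 and 11.3.7 do for the PSQI global score and the WHO-5 total. That analysis is the MMRM on change in the double-blind phase (SAP 11.1.1) and a paired t-test against baseline in the open-label phase (SAP 11.3.1).

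**The concern.** For CSDI or SDQ a change of informant changes the rater, but the child remains the one measured. For ESS, PSQI and WHO-5 a change of informant changes the person measured. If the mother answers at Visit 2 and the father at Visit 4, subtraction gives father minus mother, which is not a change in either of them. A paired t-test presumes that the same unit was measured twice, and here it would not have been.

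The scales are scheduled at Weeks 0, 2, 5, 15, 28, 41, 54, 106 and 108, so it is foreseeable that a different adult brings the child to some visits. What is at stake is the precision of three exploratory comparisons in the randomised phase and the meaning of the open-label tests against baseline, which have no concurrent control.

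**Working it through.** **Text check.** The plan states no figure on this point, so there is none to reproduce. The question is whether any rule fixes the respondent or uses the respondent field.

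- Visit instructions (Protocol 8.3 to 8.19), Table 5-2 footnotes, Table 8-1 and Appendices 7 to 9: the input comes from the parent or caregiver. There is no same-adult rule.
- Baseline and change rules (SAP 9.3 and Section 11): no condition on the respondent.
- MMRM (SAP 11.1.1): terms for treatment, visit and baseline, with treatment and baseline also nested in visit. There is no respondent term.
- Open-label paired t-test (SAP 11.3.1): tests the change score as derived.
- Listings 16.2.6.10 to 16.2.6.12 cover the three scales by subject, but no table or sensitivity analysis uses the respondent.

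So the plan neither prevents a switch nor handles one.

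**Loss of precision (illustration).** The documents give neither a switching rate nor correlations. Assume a within-person correlation of 0.75, a correlation of 0.2 between two adults of one family, and a share s of families whose respondent differs from baseline.

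- Mixed correlation: r = (1 - s) × 0.75 + s × 0.2, which is 0.695, 0.640 and 0.585 for s = 0.1, 0.2 and 0.3.
- Baseline-adjusted residual variance ratio: (1 - r²)/(1 - 0.75²) = 1.18, 1.35 and 1.50. The standard error rises by 9%, 16% and 23%.
- Variance ratio of the raw change: (1 - r)/(1 - 0.75) = 1.22, 1.44 and 1.66. The standard error rises by 10%, 20% and 29%.
- Over within-person correlations of 0.6-0.8, between-adult correlations of 0-0.4 and 10-30% switching, the variance ratio of the raw change runs from 1.05 to 2.20.

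**Open-label paired test when nobody changes (illustration).** Take n = 90, the number the sample-size section requires to complete Visit 5. Assume an ESS SD of 4.5 and replacement adults who score d points lower on average. The mean change is then -s × d, and the variance of one change is 2(1 - r) × 4.5² + s(1 - s) × d².

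For s = 0.2 and d = 2: 2 × 0.36 × 20.25 + 0.16 × 4 = 14.58 + 0.64 = 15.22, so the SD is 3.90 and the standard error is 3.90/√90 = 0.411. The spurious mean is 0.40, giving a noncentrality of 0.40/0.411 = 0.97. A two-sided 5% t-test then rejects about 16% of the time by the noncentral t and 15% by simulation.

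Approximate type I error:

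| Mean shift in replacement adults | 10% switch | 20% switch | 30% switch |
|---|---|---|---|
| 0 points | 5% | 5% | 5% |
| 1 point | 6% | 8% | 10-11% |
| 2 points | 8% | 15-16% | 26-27% |

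Where two values appear, the lower is from simulation and the upper from the noncentral t. With n = 50, the minimum expected to complete the second open-label period, a 2-point shift gives about 7%, 11% and 17% by the noncentral t.

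**The case against.** Five points can be made on the other side.

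1. **Nothing shows that respondents switch.** A reader might infer that these endpoints will contain false changes. The documents do not support that. The form field records who answered and says nothing about switching, and much of the text reads as though one caregiver per child is meant. What stands is that a switch is neither prevented nor handled.
2. **The large type I errors depend on one scenario.** A reader might take 8-26% as the expected error. It needs every replacement adult to average 2 ESS points (2/4.5 = 0.44 SD) away in one direction. No document supports that shift, and with no shift, or with switches that cancel, the error stays at about 5%.
3. **Low stakes.** All three scales are exploratory. They feed no primary or secondary endpoint, no sample size and no dose decision. The main report includes open-label data only to Visit 5. An uncontrolled before-after p-value is already weak evidence of a treatment effect. All of this is correct.
4. **A switch of category is already visible** in the recorded field. That is true, but a switch within the caregiver or other category can be missed, and leaving the handling until after unblinding makes it a post-hoc choice.
5. **A same-respondent subset should not become the main analysis.** Who attends a later visit is a post-randomisation event and may depend on family strain or on the child's sleep, so dropping those records could introduce selection. This stands and shapes the fix.

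**Conclusion.** The gap is real but minor. By the plan's own rules, a change score on ESS, PSQI or WHO-5 is a difference between two people whenever the answering adult differs from baseline, and no analysis would show it. How often that would occur is unknown.

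In the randomised phase, switching unrelated to arm costs precision: about 9-23% on the standard error under the assumed correlations and 10-30% switching. Only switching related to arm would bias the comparison. In the open-label tests the mean change is biased only if replacement adults differ systematically. The type I error then runs from about 5% (no shift) through 6-11% (1 point) to 8-26% (2 points) at n = 90. Switching rates, correlations, SD and shifts are all assumptions. The TST result and every secondary endpoint are unaffected.

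**What to change.** **Protocol Section 8 and Table 8-1.** State that the adult who answers ESS, PSQI and WHO-5 at Visit 2 answers them at later visits where possible. Require any switch to be recorded by person, because the present field gives only a category.

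**SAP 11.3.5 to 11.3.7.** Tabulate respondent switches by arm and visit. Add a pre-specified sensitivity analysis limited to change scores from the same respondent as at baseline. Keep the all-respondent analysis as the main one.

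**Cost.** One sentence and one identifying entry per form at the sites, one table and one extra run in the SAP. The sensitivity run will have fewer records and should be read with the selection caveat above.

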Full Analysis Set (FAS)	All patients in the Safety Analysis Set who satisfy all major entry criteria and who have efficacy data for the primary parameter recorded for baseline and at least 1 post-baseline period assessment
Per Protocol Set	All patients in the FAS for whom there were no serious violations of the protocol

LIST OF ABBREVIATIONS

AE	adverse events
ANCOVA	analysis of covariance
ASD	Autism Spectrum Disorder
BMI	Body mass index
CGAS	Children Global Assessment Scale
CSDI	Composite Sleep Disturbance Index
CSR	clinical study report
DSM-5/4	Diagnostic and Statistical Manual of Mental Disorders, Fifth Edition (Text Revision)
DSMB	Data Safety Monitoring Board
EC	Ethics Committee
eCRF	electronic case report form
EDC	electronic data capture
ESS	Epworth Sleepiness Scale
EU	European Union
FAS	Full Analysis Set
GCP	Good Clinical Practice
ICD-10	International Classification of Diseases
ICF	informed consent form
ICH	International Conference on Harmonization
ICSD	International Classification of Sleep Disorders
IEC	Independent Ethics Committee
IMP	Investigational Medicinal Product
IR	immediate-release
IRB	Institutional Review Board
MMRM	mixed-effect repeated measures model
PI	Principal Investigator
PIP	Pediatric Investigational Plan
PR	prolonged-release
PSQI	Pittsburgh Sleep Quality Index
SAE	serious adverse event
SAP	statistical analysis plan
SB	single blind
SD	standard deviation
SDQ	Strength and Difficulties Questionnaire
SMS	Smith-Magenis syndrome
SSRI	selective serotonin reuptake inhibitor
TESS	Treatment-Emergent Signs and Symptoms Questionnaire
TST	total sleep time
WHO-5	World Health Organization Well-Being Index

3 INTRODUCTION

Sleep disturbance is 1 of the most common complaints in children with autism spectrum disorder (ASD), mental retardation or other developmental delays¹⁻³. High prevalence for moderate sleep disturbances in these children populations is associated with significant sleep problems and subsequent distress for the families of these children, which in many cases, lead to the decision to institutionalize the children⁴. Specifically, a frequent cause of families giving up their care is discontinuous sleep with frequent awakenings throughout the night. There is a growing body of evidence on abnormal melatonin secretion in children with neurodevelopmental disorders⁵, which prompted the use of melatonin to treat sleep disorders in these populations. Several exploratory studies and case reports have led to strong consensus among researchers that exogenous melatonin is beneficial for treating chronic sleep disturbances of children who have neurodevelopmental and neuropsychiatric difficulties. Although in none of these studies significant adverse events (AEs) as a result of melatonin use have been reported, the safe, appropriate dosing (including amounts and timing), have not been established for children. Moreover, in many cases, immediate-release (IR) melatonin preparations that are available as food supplements in the USA were used. These formulations did not improve total sleep time (TST) and sleep maintenance, which are the most disturbing parameters for families⁶. As melatonin has a very short half-life (40 minutes), prolonged-release (PR) formulations are sought to cover the night period, and should affect sleep maintenance.

Circadin[®] is a 2 mg PR melatonin formulation that mimics the physiological secretion profile of melatonin and can offer more sustained blood levels of melatonin overnight. Circadin[®] 2 mg is the first, fully developed melatonin pharmaceutical product and was approved for marketing in the European Union (EU) in 2007 for the treatment of primary insomnia in patients aged 55 years and older⁷.

Several published studies performed in Canada⁸⁻¹⁰ and France⁸⁻¹⁴ have looked at the use of Circadin[®] to treat sleep wake cycle disturbances in children with neurodevelopmental disabilities. The efficacy and safety of Circadin[®] was evaluated in 42 children with chronic sleep-wake cycle disorders¹⁰. All 42 patients had severe neurodevelopmental difficulties. Initially, a randomized, double-blinded, cross-over design was used in 16 children, comparing the effectiveness of IR and PR Circadin[®]. In the remainder of the patients, the PR melatonin was studied on a clinical basis. The effectiveness of treatment was assessed by sleep charts and clinical follow-up. Emphasis was placed on the judgment of the parents, who had guidance from the physicians. The average final PR melatonin dose in the 42 patients was 5.7 mg (2 to 12 mg). The studies showed that the IR melatonin was most effective when there was only delayed sleep onset, but PR formulations were more useful for sleep maintenance.

Data from 44 children with neurodevelopmental disabilities and treatment-resistant circadian rhythm sleep disorders who had participated in the placebo controlled, double-blind cross-over trial of PR-melatonin (not Circadin[®]) were reported in a prospective follow-up study⁹. The follow-up study involved a structured telephone interview of caregivers every 3 months for up to 3.8 years. Adverse reaction to melatonin therapy and development of tolerance were not evident. Better sleep was associated with reported improvement in health, behavior, and learning. At the end of the study, the

parental comments regarding the effectiveness of long-term melatonin therapy were highly positive. Parents whose children had sleep maintenance difficulties expressed a wish to have a commercially available PR-melatonin product which would promote sleep for 8 to 10 hours.

Treatment with Circadin[®] was reported in children who presented with Smith-Magenis syndrome (SMS), mental retardation, encephalopathy, autism, Angelman syndrome, Rett syndrome, Bourneville syndrome, blindness, and delayed-sleep-phase syndrome¹². Patients aged 3 to 18 years were given Circadin[®] (4 to 6 mg/day) as a single evening dose over a treatment duration which ranged from 6 to 72 months. In the group of children for whom there were full reports by their parents (49 children) within 3 months, sleep latency with Circadin[®] decreased by 44.0% (p-value <0.001); sleep duration increased by 10.1% (p-value <0.001); and the number of midnight awakenings decreased by 75% (p-value <0.001) compared with baseline. Additionally, sleep quality improved by 75% compared with baseline (2.1±0.34 vs. 1.2±0.4, respectively, p-value <0.001). No serious adverse events (SAEs) or treatment related co-morbidities were reported. Other studies using PR-melatonin¹⁵ (not Circadin[®]) indicated long-term effectiveness of PR-melatonin at a maximal dose of 4 mg in children 4 years or less and 6 mg over this age. In children aged 2.6 to 9.6 years with autism without other coexistent pathologies, PR-melatonin was evaluated openly. Treatment gains were maintained at 12 and 24-month follow-ups. It was concluded that PR melatonin may provide an effective and well-tolerated treatment for autistic children with chronic sleep disorders.

In order to establish the efficacy and safety of Circadin[®] in children with neurodevelopmental disorders and to determine the dose, this randomized, placebo-controlled study is planned to evaluate the efficacy of a double-blind, 13-week treatment period with Circadin[®] 2/5 mg in improving maintenance of sleep, sleep latency and additional parameters in children with neurodevelopmental disabilities. The efficacy and safety of Circadin[®] 2/5 mg will continue to be assessed during an open-label extension period of 13 weeks. Withdrawal effects will also be assessed during the 2-week single-blind (SB) placebo run-out period.

